5.4.2 Clinical Laboratory Variables

Refer to protocol sections 7.2.2 and protocol appendix 12.7 for a table of the laboratory tests that will be performed during the conduct of the study. Refer to the protocol schedule of assessments for the evaluations' schedule.

5.4.3 Vital Signs, Height and Weight

Vital signs will include blood pressure (systolic blood pressure (SBP) and diastolic blood pressure (DBP)), pulse and respiratory rate. Vital signs, height and weight will be measured as indicated by the protocol schedule of assessments.

5.4.4 Routine 12-lead electrocardiograms

A routine 12-lead ECG will be performed at the time points outlined in the protocol schedule of assessments. ECGs will be taken in triplicate.

To calculate QTcF (corrected QT interval using Fridericia's formula) the following formula will be applied:

$$QT_CF = \frac{QT}{\sqrt[3]{\frac{RR}{1s}}}$$

5.4.5 Physical Examination

Physical examinations will be performed as indicated in the protocol schedule of assessments and whenever there is a medical indication. On day 1 (pre- and postoperatively) and at the follow-up visit, a symptom-directed physical examination will be performed. If clinically significant worsening of findings from baseline is noted, the changes will be documented as AEs on the AE eCRF.

5.5 **Other Endpoints**

5.5.1 Pharmacokinetic Endpoints

Pharmacokinetic endpoints are:

- Plasma and urine concentrations of ASP5354
- Amount of ASP5354 excreted in urine (Ae) during surgery
- Percentage of ASP5354 excreted into urine (Ae%) during surgery

5.5.2 Pharmacodynamic Endpoints

Pharmacodynamic variables will include the primary endpoint (anatomical visualization of the index ureter) and exploratory efficacy endpoints (Likert Scale, visualization duration and SBR).

5.5.3 Green Discoloration of Urine

The incidence and the duration of green discoloration of urine will be analyzed. It will be recorded any time after dose administration. If it occurs, the color of urine will be assessed during surgery and every 120 minutes (\pm 30 minutes window) after the end of surgery until it resolves or the subject is discharged, whichever is earlier. The start and stop date and time will also be recorded.

6 STATISTICAL METHODOLOGY

6.1 General Considerations

Continuous data will be summarized descriptively including the number of subjects, mean, standard deviation (SD), median, minimum and maximum. In addition, for continuous PK variables, and PK parameters, coefficient of variation (%CV), geometric mean (GM), and geometric coefficient of variation (Geo %CV) will also be calculated. GM and Geo %CV will not be calculated if at least one value is below the quantification limit (BQL). Categorical data will be summarized by frequencies and percentages. Percentages by categories will be based on the number of subjects with no missing data, i.e. the percentages for the non-missing categories will add up to 100%. All non-coded free-text variables will be displayed in data listings only.

Summaries based on FAS (e.g., disposition, baseline characteristics and efficacy endpoints), safety summaries based on SAF and summaries based on PKAS will be presented by actual treatment dose received.

All data summarization and analyses will be performed using SAS® Version 9.4 or higher on Red Hat Enterprise Linux. Specifications for table, figures, and data listing formats can be found in the TLF specifications document for this study.

Unless otherwise specified, all summaries will be presented by dose group. Subjects who were randomized before determination of optimal dose are grouped by the dose received. Additional subjects who were enrolled after determination of optimal dose are in a separate group. Apart from the overall group, a separate overall group for the optimal determined dose will be presented when specified in the TLF specifications document.

6.2 Study Population

In general, data such as patient disposition, demographics and baseline characteristics will be summarized for FAS and SAF by dose group and overall, unless specifically stated otherwise. In the event when FAS is identical to SAF (i.e., all randomized subjects have at least 1 assessment of ureter visualization during surgery), then these data summaries will not need to be repeated for SAF.

6.2.1 Disposition of Subjects

Disposition of subjects will be summarized for the FAS and SAF by dose group and overall, unless otherwise specified. The following analyses will be performed:

- Number and percentage of subjects with informed consent, discontinued prior to randomization (screen failures), randomized for all subjects with informed consent.
- Number and percentage of subjects who were randomized, took IP, did not take IP (including the reason why IP was not taken), in each analysis set by dose group and overall for all randomized subjects.
- Number and percentage of subjects who completed/discontinued the screening period, and primary reason for discontinuation for all subjects with informed consent.
- Number and percentage of subjects who completed and discontinued the study, and primary reason for discontinuation by dose group and overall for all randomized subjects, FAS and SAF.

6.2.2 **Protocol Deviations**

The number and percentage of subjects with the following important protocol deviation criteria will be summarized for each criterion and overall, by dose group and total as well as by investigative site, for all randomized subjects. Subjects deviating from a criterion more than once will be counted once for the corresponding criterion. Any subjects who have more than one important protocol deviation will be counted once in the overall summary.

The unique identifiers will be as follows:

- PD1 Inclusion/Exclusion,
- PD2 Withdrawal Ciriteria,
- PD3 Study Intervention,
- PD4 Excluded Concomitant Medication,
- PD5 Informed Consent,
- PD6 Safety Reporting,
- PD7 Procedures/Tests.

A data listing will be provided by investigative site and subject.

6.2.3 Demographic and Other Baseline Characteristics

Demographic variables (sex, age, ethnicity, race), age categories (>=18 to <65, >=65), EudraCT age categories (>=18 to <65, <=65 to <85, >=85), height, weight and body mass index (BMI), BMI categories (< 25, >=25 to <30, >=30 to <40, >=40) will be summarized by dose group and overall for FAS and SAF.

Medical history is coded in Medical Dictionary for Regulatory Activities (MedDRA), and will be summarized by System Organ Class (SOC) and Preferred Term (PT) by dose group and overall for the SAF.

Drug and alcohol history and medical history for each subject will be listed.

6.2.4 Previous and Concomitant Medications

Previous medications are defined as medications that patients started and ended prior to IP administration. Concomitant medications are defined as any medications that patients took at or after the day of IP administration. Medications that started prior to IP administration and continued after IP administration will be counted in both previous and concomitant medications.

Previous and concomitant medications will be summarized in separate tables by therapeutic subgroup (anatomical therapeutic chemical (ATC) 2nd level) and chemical subgroup (ATC 4th level) and preferred world health organization (WHO) name by dose group and overall for the SAF. Subjects taking the same medication multiple times will be counted once per medication. A medication that can be classified into several chemical and/or therapeutic subgroups is presented in all chemical and therapeutic subgroups.

All previous and concomitant medications will be presented in a listing.

6.2.5 Non-medication Therapies

The frequency and percentage of subjects with previous and/or concomitant non-medication therapies will be summarized along with the reason for use for SAF by dose group and overall.

All non-medication therapies will be presented in a listing.

6.3 Study Drugs Exposure and Compliance

Since this is a single dose study, the analysis of duration of exposure is not applicable.

Study drug dosing information which includes dosing date and time, total volume prepared and actual volume administered in ml, total test drug used in mg and the compliance in % will be listed only.

6.4 Analysis of Efficacy

Efficacy analyses will be conducted on the FAS. No hypothesis testing will be performed.

6.4.1 Analysis of Primary Efficacy Endpoint

The primary endpoint is the anatomical visualization of the index ureter(s) 30 minutes after dosing of ASP5354 and the end of surgery.

6.4.1.1 Primary Analysis for Primary Efficacy Endpoint

The success rate of anatomical visualization of the index ureter(s) at 30 minutes after dosing and end of surgery, will be estimated with exact 95% confidence interval (CI) by dose group.

SAS code for constructing 95% confidence interval for the success rate by Clopper-Pearson method is given as follows:

proc freq;

```
tables success / binomial (level='1');
```

exact binomial;

run;

where the numerical variable success is either 1, in case of success, or 0 otherwise.

6.4.1.2 Secondary Analysis for Primary Efficacy Endpoint

The frequency and percentage of anatomical visualization of the index ureter(s) will be summarized by dose group and all assessed time points (including 30 minutes after dosing and end of surgery).

6.4.2 Analysis of Secondary Efficacy Endpoints

Since no efficacy endpoint is specified as secondary endpoint, it is not applicable.

6.4.3 Analysis of Exploratory Efficacy Endpoints

Exploratory efficacy endpoints are listed in Section 5.5.

The Likert Scale of the intensity of the fluorescence will be summarized by frequency and percentage by dose group and time point for index ureter(s), and if applicable, for the contralateral ureter.

The duration of anatomical visualization of the index ureter(s) will be summarized using descriptive statistics by dose group. The duration of anatomical visualization of the index ureter(s) in minutes will be from the first time of positive visualization to the last time of positive visualization:

$$Duration = last time - first time + 1$$

If there are missing assessments of the anatomical visualization, then the last observed time of positive visualization will be used.

Based on fluorescence images recorded during the entire surgery (predose and approximately 10, 20, 30, 45 and 60 minutes postadministration of ASP5354, and then every 30 minutes thereafter and/or at the last time point before removal of visualization instruments), the SBR will be derived as follows:

$$SBR = \frac{mean \ region \ of \ interest}{mean \ signal \ background}$$

based on Hoogstins et al, 2019. The SBR for index ureter(s) will be summarized using descriptive statistics by dose group and time point.

The investigator will be asked the following questions:

- Was the location of the index ureter(s) as expected (Yes or No)?
- Did visualization of the index ureter(s) occur with white light at 30 minutes after ASP5354 administration (Yes or No)?
- Did visualization of the index ureter(s) occur with white light at the end of surgery (Yes or No)?

- Was NIR-F superior to white light in terms of visualization of the index ureter(s) (Yes or No)?
- Did the location of the ureter visualized by NIR-F alter the operative plan (Yes or No)?
- Were any ureter anomalies or abnormalities observed (Yes or No)?

These binary questions for the benefit will be summarized by frequency and percentage by dose group.

The success rate of anatomical visualization of the contralateral ureter at 30 minutes after dosing and end of surgery will be estimated with exact 95% CI by dose group (for SAS code, see Section 6.4.1.1), if applicable. In addition, the frequency and percentage of anatomical visualization of the contralateral ureter will be summarized by dose group and time point, if applicable.

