7.1.2.2 Duration of Ureter Visualization

Intraoperative ureter fluorescence visualization will be assessed at approximately 10, 20, 30, 45 and 60 minutes postadministration of ASP5354, and then every 30 minutes thereafter and/or at the last time point before removal of visualization instruments (end of surgery). The duration of visualization of the index ureter(s) will be based on the result from the first positive visualized time point to the last positive visualized time point. Images will be captured on a bright field, NIR-F and overlay view (if available). The contralateral ureter will also be visualized when feasible, per the investigators judgment, at similar time points.

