4.1 Full Analysis Set

The full analysis set (FAS) will consist of all subjects who receive ASP5354 and have at least 1 assessment of ureter visualization during surgery. This will be the primary analysis set for efficacy analyses.

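### Visualization duration (first Yes to last Yes) counts observed No time as visualized and gives no value to subjects never visualized, so the dose-group summary is conditional on being visualized

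*SAP*

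**What the plan says.** Protocol 7.1.2.2 bases duration on the result "from the first positive visualized time point to the last positive visualized time point". SAP 6.4.3 repeats the span, stating that the duration "will be from the first time of positive visualization to the last time of positive visualization", and gives the formula "Duration = last time - first time + 1", in minutes. Readings are scheduled at "approximately 10, 20, 30, 45 and 60 minutes postadministration of ASP5354, and then every 30 minutes thereafter", with a last reading at the end of surgery.

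The analysis is purely descriptive: "The duration of anatomical visualization of the index ureter(s) will be summarized using descriptive statistics by dose group". Section 6.4.3 has one handling rule for this variable: "If there are missing assessments of the anatomical visualization, then the last observed time of positive visualization will be used". It covers readings that were not made. It does not mention a reading of No between two Yes readings, or a subject with no Yes at all.

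Efficacy is analysed on the FAS, which is "all subjects who receive ASP5354 and have at least 1 assessment of ureter visualization during surgery" (SAP 4.1). A subject assessed throughout and never visualized is therefore in the FAS. SAP 6.10 sets a general principle of no imputation; its exceptions are incomplete dates and the 30-minute reading of the primary endpoint.

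Duration has a second use. SAP 5.5.2 lists as pharmacodynamic variables the primary endpoint and "exploratory efficacy endpoints (Likert Scale, visualization duration and SBR". The protocol synopsis names visualization duration among the measures to be related to pharmacokinetics in the population PK/PD analysis.

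**The concern.** A duration summary by dose should let a reader see how long the ureter could be seen at each dose. Under this rule the number answers a narrower question: among subjects seen at least once, how far apart were the first and last sightings? That can differ from time visualized in two ways:

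- **(a) Gaps.** A subject whose signal is lost and later returns scores the same as one visualized throughout.
- **(b) Never visualized.** The worst outcome on this variable is removed from the average rather than scored as the worst. A dose that fails in most subjects can report the same mean and median as one that works in all of them.

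Duration is tied to an exploratory objective, and the dose rationale in Protocol 4.2 rests on an expected 3 hours of sufficient visualization. This variable is the natural check on that expectation. If the same derivation enters the PK/PD dataset, the failures would be missing from the exposure-response relationship for duration.

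**Working it through.** The plan states no duration figure, so there is nothing to reproduce. The check applies the SAP 6.4.3 formula to response patterns on the documented schedule.

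**(a) Gaps.** Take Yes at 10 minutes, No at 20, 30, 45, 60 and 90, and Yes at 120.

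- SAP duration: 120 − 10 + 1 = 111 minutes, with Yes at 2 of 7 readings.
- Yes at all seven readings: also 120 − 10 + 1 = 111 minutes.
- Longest unbroken run of Yes in the first pattern: 10 − 10 + 1 = 1 minute.
- If Yes holds from 10 minutes to some time and is No afterwards, span and unbroken run are identical, so the gap error is 0.

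**(b) Never visualized.** Let n be the FAS subjects in a dose group, k the number with at least one Yes, and S the sum of their durations.

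- Mean by the SAP formula: S/k, because the other n − k have no value.
- Mean with never-visualized subjects at 0: S/n.
- Ratio: (S/k)/(S/n) = n/k = 1/(fraction visualized). The equal durations below only keep the arithmetic simple.

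| Assumed group of 15 | Mean, visualized only | Mean with zeros | Ratio |
|---|---|---|---|
| 3 visualized, 120 min each | 120 | 3 × 120/15 = 24 | 15/3 = 5.0 |
| 5 visualized, 51 min each | 51 | 5 × 51/15 = 17 | 15/5 = 3.0 |
| 10 visualized, 81 min each | 81 | 10 × 81/15 = 54 | 15/10 = 1.5 |
| 15 visualized, 171 min each | 171 | 171 | 1.0 |

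In the first row the median moves from 120 to 0, since 12 of 15 values become 0.

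**How both effects vary with response.** For illustration only, assume a 180-minute surgery, readings at 10, 20, 30, 45, 60, 90, 120, 150 and 180 minutes, and an independent probability p of Yes at each. All 2^9 = 512 patterns were enumerated. The comparator adds the intervals with Yes at both ends, plus 1 minute, and scores 0 for never visualized.

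| p | SAP mean (min) | Span, with zeros | Comparator | Excess from gaps | Excess from omission |
|---|---|---|---|---|---|
| 0.1 | 30.9 | 18.9 | 2.3 | 16.6 | 12.0 |
| 0.3 | 89.1 | 85.5 | 16.3 | 69.3 | 3.6 |
| 0.5 | 130.6 | 130.3 | 43.5 | 86.8 | 0.3 |
| 0.7 | 153.7 | 153.7 | 84.3 | 69.4 | 0.0 |
| 0.9 | 166.6 | 166.6 | 138.7 | 27.9 | 0.0 |
| 1.0 | 171 | 171 | 171 | 0 | 0 |

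(Differences may be off by 0.1 from rounding.) The ratio of SAP mean to comparator falls from 13.4 at p = 0.1 to 3.0 at p = 0.5 and 1.0 at p = 1. In minutes, the total excess is 28.6 at p = 0.1, peaks at 87.1 at p = 0.5 and returns to 0. The gap error is therefore not largest, in minutes, at the weakest response.

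**The case against.** The strongest reply is that the other outputs limit the harm, and much of it stands.

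- Descriptive statistics include the number of subjects (SAP 6.1), so the example would print n = 3 beside the 120 minutes.
- SAP 6.4.1.2 tabulates Yes frequencies at every assessed time point.
- The subject in pattern (a) is No at 30 minutes and so fails the primary endpoint.
- The endpoint is exploratory, and SAP 6.4 plans no hypothesis test.

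These outputs alert a careful reader. They do not show Yes-No-Yes patterns within subjects, and they do not correct the mean, the median or a derived PK/PD variable.

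The span is also the protocol's own, openly stated definition. That stands too: the SAP should not replace it alone and so put the two documents at odds.

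A reader might infer that the rule overstates duration most at weak doses and so tilts the dose choice downwards, since the lower dose may be chosen when two perform equally. The documents do not support this. They give no response rates by dose and do not say that intermittent signal is commoner at weak doses. The criteria named for the VRC (SAP 2.2, Protocol 4.1) are visualization at 30 minutes and end of surgery, and Likert intensity. Duration could enter only because that list is open-ended, and nothing shows that the committee uses the SAP 6.4.3 mean.

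The SAP is silent on never-visualized subjects rather than expressly excluding them. Omission is the natural result of an undefined formula with no imputation. The separate population analysis plan and the table specifications might say otherwise; neither is available here.

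A separate limit remains: a subject still Yes at the end of surgery is capped by its length (51 minutes if it ends at 60, 171 if at 180, counting from a first Yes at 10). SAP 6.8.1 censors the comparable urine-discoloration duration; 6.4.3 does not.

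**Conclusion.** The point holds for the derivation and the descriptive summary. As written, observed No time inside the span is counted as visualized, and never-visualized FAS subjects have no value.

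The second effect has a definite size: the mean is inflated by 1/(fraction visualized), five-fold in the assumed 3-of-15 case, and the factor grows as fewer subjects are visualized. This rests on reading an undefined formula as a missing value. For the first effect, neither size nor direction by dose can be fixed from the documents; it is zero when Yes readings are unbroken. A claim that the total error is greatest at weak doses holds only as a ratio under the assumed independent-response model, and fails there in minutes.

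The primary success rate and its confidence interval are untouched. What is affected is the descriptive comparison of duration between doses and, if the same derivation is carried over, the PK/PD variable.

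**What to change.** In SAP 6.4.3:

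1. Set duration to 0 minutes for FAS subjects with at least one reading and no Yes. Show the number visualized per dose group, and give the mean among visualized subjects as a labelled second line.
2. Keep the first-to-last span as the defined endpoint, so that SAP and protocol still agree. Report per dose group how many subjects have a No between two Yes readings. Add one supportive duration that does not count No time, for example the longest unbroken run of Yes, computed as last minus first plus 1. A single Yes then scores 1 minute and stays distinct from 0. Summing Yes-to-Yes intervals without the added minute would score a single Yes, and pattern (a) above, as 0, the same as never visualized. State whether a missed reading breaks a run.
3. Apply the same zero rule in the PK/PD dataset and say so in the population analysis plan.

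The cost is SAP wording and a few lines of programming; the Yes/No readings and their times are already collected. Reported durations will be shorter wherever some subjects are never visualized, and the table gains a supportive line.

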1.3.1 Sample Collection and Timed Procedure Schedule

Table 2 Sample Collection and Timed Procedure Schedule

Day	Operation	Time Point	Sample Collection		Efficacy Assessment	Collection Window
			Blood Sampling for Pharmacokinetics	Urine Point Sampling for Pharmacokinetics	Surgeon Evaluation for Ureteral Visualization	
Day 1	Preoperative	Predose	X	X	^d	Within 1 h before dosing
	Intraoperative	10 min ^a	X		X	5 min ≤ and < 15 min
		20 min ^a			X	15 min ≤ and < 25 min
		30 min ^a	(X) ^e		X	25 min ≤ and < 38 min
		45 min ^a			X	38 min ≤ and < 53 min
		60 min ^a	(X) ^e		X	53 min ≤ and < 75 min
		T min ^{a, b}			X	T-15 min ≤ and < T+15 min
	End of surgery	-	X	X ^f	X	-
Postoperative	180 min ^c	X			105 min ≤ and < 240 min	

- If end of surgery is earlier than this time point, this time point(s) would not need to be collected.
- This time point(s) would need to be evaluated every 30 minutes from 60 minutes after administration.
- In cases where the surgery is completed in less than 105 minutes, blood samples would be collected at approximately 180 minutes after administration.
- At the predose time point, fluorescence images will be captured and recorded on a bright field, near infrared fluorescence and overlay view (if available) for signal background ratio analysis, as well as the other time points.
- Either 30 or 60 minutes after administration need to be collected.
- Urine collection at end of surgery time point is optional (if a sample is available). The urine sample for the amount of ASP5354 excreted in urine during surgery will be collected from the urine in the catheter bag after the end of surgery.

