4 STUDY DESIGN AND DOSE RATIONALE

4.1 Study Design

The study is a randomized open-label, dose-ranging study in adult subjects undergoing laparoscopic/minimally invasive colorectal surgery in which the need for anatomical visualization of the ureter is anticipated. This study will be conducted at approximately 2 study sites in the US.

Subjects will be randomly assigned to receive single doses of ASP5354 (CCI, ⁹⁹ or CCI) which will be administered as an iv bolus to evaluate the anatomical visualization of the index ureter(s) (and contralateral ureter when feasible). Safety, tolerability and pharmacokinetics in the study population will also be assessed.

Up to 15 subjects will be randomly assigned at each dose level.

Dose Arm	ASP5354 Dose Level	Number of Subjects
1	CCI	Up to 15
2	CCI	Up to 15
3	CCI	Up to 15
Total	-	Up to 45

Additional Dose Arm	ASP5354 Dose Level	Number of Subjects
4	CCI	Up to 15
5	CCI	Up to 15
6	CCI	Up to 15

* Based on VRC review of the initial 3 dose levels, if none of the doses selected have visualization, then CCI and CCI dose levels will be added; if 1 dose selected has visualization, then the CCI dose level will be added. The CCI dose level will only be added if only the CCI dose level has visualization.

During a standard minimally invasive surgery, visualization of the surgical field will be assessed following the placement of the NIR-F imaging system (with FDA 510[k] cleared optical device system) proximal to the ureter of interest and then ASP5354 will be administered.

- Intraoperative ureter fluorescence visualization will be assessed at approximately 10, 20, 30, 45 and 60 minutes postadministration of ASP5354, and then every 30 minutes thereafter and/or at the last time point before removal of visualization instruments (end of surgery).
- The contralateral ureter will also be visualized when feasible, per the investigator's judgment, at similar time points. Fluorescence images will be captured on a bright field, NIR-F and overlay view (if available) and recorded during the entire surgery and archived.
- The anatomical visualization of the index ureter(s) will be assessed by the investigator intraoperatively using a binary "Yes or No" question on the ability to visualize the ureter at each time point.
- The fluorescence intensity of the ureter will be qualitatively assessed using a Likert Scale (0 = None, 1 = Mild, 2 = Moderate and 3 = Strong).

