- The duration of anatomical visualization of the index ureter(s) will be from the first time of positive visualization to the last time point of positive visualization.
- Recorded images will be used to determine the signal background ratio (SBR).

The visualization data will be assessed by a Visualization Review Committee (VRC), consisting of the investigator(s) and the sponsor's medical representative. The VRC will be held at the following time points, but ad-hoc meetings may occur until the optimal dose is determined:

- 1) after the initial 3 subjects have completed the surgical procedures at each of the dose levels; and
- 2) then in increments of 3 subjects (up to a total of 15 subjects per dose level) for those who have completed surgical procedures at the expanded dose levels.

The visualization data for the subjects, at each interim time point, who completed the surgical procedure will be assessed to decide whether to:

- 1) expand a dose under evaluation;
- 2) stop a dose under evaluation in which case additional subjects would not be added to a dose level; or
- 3) define a dose as optimal.

Once the optimal dose is determined, the optimal dose cohort may continue enrollment up to the maximum 15 subjects.

The VRC assessment to stop, to continue or to define an optimal dose level will be based on the totality of the collected data, including but not limited to the following:

- 1) anatomical visualization, defined as positive visualization of the ureter at both 30 minutes after ASP5354 administration and at the end of surgery; or
- 2) fluorescence intensity based on the Likert Scale (0 to 3).

In the case where 2 doses perform equally, the lower dose may be selected.

Based on VRC review of the initial 3 dose levels, if none of the doses selected have visualization, then **CCI** and **CCI** dose levels will be added; if 1 dose selected has visualization, then the **CCI** dose level will be added. The **CCI** dose level will only be added if only the **CCI** dose level has visualization. For further details of the VRC, refer to the VRC charter.

If the investigator judges that anatomical visualization of ASP5354 is not sufficient for the subject at 30 minutes after administration, the investigator can proceed with surgery using other modalities for visualization.

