7.1.2 Exploratory Assessments

7.1.2.1 Intensity of Fluorescence

The intensity of fluorescence will be qualitatively assessed during surgery by the investigator, by direct examination of the ureter. A Likert Scale (0 = None, 1 = Mild, 2 = Moderate and 3 = Strong) will be used to determine the intensity of fluorescence at each time point. The contralateral ureter will also be visualized when feasible, per the investigators judgment, at similar time points.

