7.1.2.3 Signal Background Ratio

Fluorescence images will be captured and recorded during the entire surgery and archived. Images will be captured on a bright field, NIR-F and overlay view (if available). SBR will be calculated using fluorescence images at predose, approximately 10, 20, 30, 45 and 60 minutes postadministration of ASP5354, and then every 30 minutes thereafter and/or at the last time point before removal of visualization instruments (end of surgery), as follows [[Hoogstins et al, 2019](#)]:

$$\text{SBR} = \frac{\text{mean region of interest}}{\text{mean signal background}}$$

Additional detail will be provided in the Imaging Charter.

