2.3 Randomization

This is an open-label study; however, enrollment, randomization and dispensation of investigational product (IP) will be performed via the interactive response technology (IRT) system.

The treatment is assigned in a 1:1:1 ratio to:

- **CCI** ASP5354
- **CCI** ASP5354
- **CCI** ASP5354

Doses of and/or **CC** will be added if needed as outlined in SAP Section 2.2. Prior to initiation of treatment, study site personnel will obtain the randomization number and treatment assignment from the IRT system. Specific IRT procedures will be described in the respective study manual.

No stratification factors will be used.

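### Predose SBR is collected for the SBR analysis, but neither the protocol nor the SAP specifies a baseline-adjusted SBR analysis

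*SAP*

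**What the plan says.** Protocol 7.1.2.3 lists predose among the SBR time points: "SBR will be calculated using fluorescence images at predose, approximately 10, 20, 30, 45 and 60 minutes postadministration of ASP5354", then every 30 minutes and/or at the end of surgery. A footnote to Table 2 (Protocol 1.3.1) gives the reason for the predose images: they are captured in bright field, near-infrared and "overlay view (if available) for signal background ratio analysis, as well as the other time points". SBR is the mean of the region of interest divided by the mean background, taken from recorded images. On the reading of those images the protocol says only "Additional detail will be provided in the Imaging Charter".

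The analysis is one sentence, the same in Protocol 9.4.3 and SAP 6.4.3: "The SBR for index ureter(s) will be summarized using descriptive statistics by dose group and time point". SAP 6.1 defines descriptive statistics as n, mean, SD, median, minimum and maximum, and adds geometric statistics for PK variables only. For laboratory values, vital signs and ECG, SAP 6.5.2 to 6.5.4 do plan change from baseline.

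The other visualization measures come from the operating investigator in an open-label study. For the binary endpoint: "The anatomical visualization of the index ureter(s) will be assessed by the investigator intraoperatively using a binary 'Yes or No' question". For the Likert score: "The intensity of fluorescence will be qualitatively assessed during surgery by the investigator, by direct examination of the ureter". Duration is derived from the binary answers.

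**The concern.** The trial obtains a drug-free SBR from each subject for the purpose of SBR analysis, then specifies no analysis that sets post-dose values against it. Post-dose SBR may partly reflect the subject's own tissue and imaging conditions. If predose SBR captures some of that, adjusting for it sharpens the comparison between doses and corrects for chance differences between small arms.

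This has some weight because SBR is the only visualization measure taken from images and not from the investigator's rating, and the primary objective is to choose a dose. SBR is also a ratio, for which logs and geometric means are the natural scale, but the SAP provides only arithmetic summaries for it.

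**Working it through.** **The plan's own figures.** The SAP states no figure for SBR. Its sample-size maxima reproduce: 3 × 15 = 45 and 6 × 15 = 90 (SAP 3). There is no power, alpha or SD of SBR to reproduce.

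**Inputs.** Up to 15 subjects per dose (SAP 3). The three initial doses are randomized: "The treatment is assigned in a 1:1:1 ratio to" these doses (SAP 2.3), with no stratification. About 2 sites (Protocol 4.1). A dose may stop after its first 3 subjects (Protocol 4.1). Two quantities are not in the documents and are assumed over a range: ρ, the within-dose correlation of log predose and log post-dose SBR, and k = SD(log predose) / SD(log post-dose).

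**Variance of a dose difference, relative to raw log SBR (= 1).**
- Covariate model: 1 − ρ².
- Log ratio to predose: 1 + k² − 2ρk, which is 2(1 − ρ) when k = 1.
- Log ratio minus covariate model: (1 + k² − 2ρk) − (1 − ρ²) = (k − ρ)², which is never negative. On this measure the ratio never beats the covariate model.

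| ρ | Covariate model | Log ratio, k = 1 | Log ratio, k = 0.25 | 15 subjects count as: covariate, 15/(1 − ρ²) | 15 subjects count as: log ratio, k = 1 |
|---|---|---|---|---|---|
| 0 | 1.00 | 2.0 | 1.06 | 15.0 | 7.5 |
| 0.3 | 0.91 | 1.4 | 0.91 | 16.5 | 10.7 |
| 0.5 | 0.75 | 1.0 | 0.81 | 20.0 | 15.0 |
| 0.7 | 0.51 | 0.6 | 0.71 | 29.4 | 25.0 |

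**Width of the interval.** The 95% half-width for two arms of n, in post-dose SD units, is t × √(2/n) raw, with 2n − 2 degrees of freedom. With the covariate it is t × √((1 − ρ²) × 2/n), with 2n − 3. This leaves out the small extra variance caused by chance predose imbalance.
- n = 15: raw 2.048 × 0.365 = 0.75. Covariate 0.72, 0.65 and 0.54 at ρ = 0.3, 0.5 and 0.7.
- n = 3: raw 2.776 × 0.816 = 2.27. Covariate 2.48, 2.25 and 1.86. At ρ = 0.3 the lost degree of freedom costs more than the covariate returns.

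**Chance imbalance.** Assuming two equal sites and no stratification, the SD of the between-arm difference in site share is √(2 × 0.25/15) = 0.18 at 15 per arm and √(2 × 0.25/3) = 0.41 at 3 per arm. This is random variation with mean zero.

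**Camera settings.** With illustrative signals of 100 (ureter) and 20 (background), SBR is 5.0 at gain 0.5, 1 or 2, so a pure gain cancels within SBR. An additive offset of 20 gives 2.33, 3.00 and 3.67 at those gains. In the same example predose SBR, with ureter and background both at 20, is 1.0 throughout, so relating SBR to predose would not remove the offset.

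**The case against.** **The baseline is in the plan already.** A reader might infer that predose SBR is collected and then discarded. The documents do not show that. Predose is a listed SBR time point, so a summary by time point would naturally include it. The SAP 6.10.1 window table has no predose row, but it is stated for anatomical visualization only. SBR is also a pharmacodynamic variable (Protocol 7.5, SAP 5.5.2), and the PK/PD modelling has its own plan, which we do not have; nor do we have the Imaging Charter. What stands is narrower: no baseline-adjusted analysis is specified in the protocol or SAP.

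**Camera and site differences do not bias the comparison.** A reader might infer that they do. The documents describe the device only as a cleared optical system and do not say that devices differ. Gain cancels, and an offset need not be repaired by a predose image. Among randomized doses the rest is noise and chance imbalance. This defence does not extend to subjects enrolled after the optimal dose is determined. They enter under different BMI and eGFR criteria and form a separate group, so differences from them can be systematic.

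**SBR may not be independent of the surgeon.** This is correct. Neither document says who reads the images or whether the reader knows the dose.

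**Adjustment may gain nothing.** This is fair. Without dye, predose SBR may sit near 1 and predict little. At ρ = 0 the covariate model gains nothing and the ratio at equal SDs doubles the variance. This argues against comparing doses on the ratio, and for the covariate model, whose cost at 15 per arm is about one degree of freedom.

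**The endpoint is exploratory.** It is, no hypothesis testing is planned, and SBR is not one of the two criteria named for the Visualization Review Committee, although that list is open-ended. This limits the weight of the point but does not remove it.

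**Conclusion.** The concern holds in a limited form. The trial collects predose SBR for the SBR analysis, and neither Protocol 9.4.3 nor SAP 6.4.3 specifies an analysis that adjusts for it. SBR is summarized raw, with arithmetic statistics. The loss is one of precision and uncorrected chance imbalance among randomized doses. At 15 per arm it ranges from nothing (ρ = 0) to about half the variance (factor 0.51 at ρ = 0.7). Those figures rest on assumed correlations and, for the ratio, an assumed SD ratio; the documents supply neither. They also use 15 per arm, which is a maximum. Severity is low.

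**What to change.** In SAP 6.4.3, for the final analysis only:

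1. Keep the raw SBR summary by dose group and time point, and state that it includes a predose row.
2. Estimate dose differences at 30 minutes and end of surgery from a linear model of log SBR on dose group with log predose SBR as covariate. Report back-transformed ratios with 95% CIs and no tests, which is compatible with the no-testing statement in SAP 6.4. Label any contrast with the group enrolled after optimal dose determination as non-randomized.
3. Show the geometric mean of SBR(t)/SBR(predose) by dose group and time point as supportive description, not as the basis for comparing doses.
4. Leave doses that stopped at 3 subjects to the raw summary.
5. State who reads the images and whether the reader is blinded to dose, or refer to the place in the Imaging Charter that says so.

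The cost is SAP wording and one table, with no new data. The model uses one degree of freedom, and subjects without a usable predose image drop out of the added analyses only.
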